8.7 End of Study visit

8.7.1 Day 91 (± 2) Visit 8

At the end of study visit, subjects will return with their medication bottle. The following assessments will be undertaken:

- Weight
- Vital signs
- Targeted physical examination
- Concomitant medications
- Blood and urine samples for safety analysis (haematology, clinical chemistry, urinalysis)
- Adverse events

8.8 Early withdrawal visit

Subjects who do not complete the study will be asked to return for an End of Study visit (Section 8.7.1). This visit should be scheduled approximately two weeks after the last dose was taken.

9. Study Endpoints

9.1 Primary endpoint

Absolute change in mean pain score, using an 11 point NPRS, from baseline to the last week of
each treatment period. Pain is recorded once daily in a subject diary in the evening, and should
reflect the subject's average pain over the last 24 hours

Baseline mean pain for each subject is defined as the mean of the last five available ratings of daily pain, recorded in each baseline period.

End of treatment mean pain for each subject is defined as the mean of the last five available ratings of daily pain, recorded in the last 7 days of each 4 week treatment period.

9.2 Secondary endpoints

- Change in NPRS score at 0.5, 1, 2, 4 and 6 hours after the first dose of IMP in each treatment period, compared with the score recorded no more than 60 minutes before the first dose of IMP in that treatment period (PK subjects only)
- Change in NPRS score at 0.5, 1, 2, 4 and 6 hours after a single dose of IMP, following four
 weeks treatment with IMP in each treatment period, compared with the score recorded no more
 than 60 minutes before this dose (PK subjects only)
- Change in mean pain scores from baseline after 1, 2 and 3 weeks of dosing with IMP in each
 treatment period, using an 11 point NPRS. Pain scores at weeks 1, 2 and 3 are defined as the
 mean of the last five available ratings of daily pain in the subject diary, recorded in the previous 7
 days of treatment
- 30% responder rate, based on the proportion of subjects achieving ≥ 30% reduction in mean NPRS from baseline to the end of 4 weeks treatment in each treatment period
- 50% responder rate, based on the proportion of subjects achieving ≥ 50% reduction in mean NPRS from baseline to the end of 4 weeks treatment in each treatment period
- Maximum change in mean NPRS from baseline after 1, 2, 3 or 4 weeks treatment in each treatment period
- Change in functioning from baseline to the end of 4 weeks treatment in each treatment period, as measured by the BPI interference scale
- Change in pain characteristics and intensity from baseline to the end of 4 weeks treatment in each treatment period, as assessed by the SF-MPQ-2
- Change in neuropathic pain symptoms from baseline to the end of 4 weeks treatment in each treatment period, as assessed by NPSI
- Change in emotional functioning from baseline to the end of 4 weeks treatment in each treatment period, as assessed by the BDI-II
- PGIC at the end of each four week treatment period
- Paracetamol (rescue medication) use per week over each treatment period compared with the preceding baseline

9.3 Safety endpoints

- Physical examinations and vital signs
- ECG
- Clinical chemistry and haematology analyses

- Urinalysis
- Number and type of Treatment Emergent Adverse Events (TEAEs), including serious adverse events (SAEs), and suspected unexpected serious adverse reactions (SUSARs)
- Concomitant medications

9.4 Pharmacokinetic endpoints

• Pharmacokinetic parameters: C_{max}, T_{max}, AUC_{0-inf} in each treatment period, after a single dose and at the end of four weeks treatment in PK subjects

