On Day 14 (Visit 3), subjects will take their morning IMP dose and return to the clinic. Weight, vital signs, a targeted physical examination, concomitant medications and adverse events will be recorded. Subject compliance with medication and diary entries will be checked. Subjects will be reminded to continue their medication and to record daily entries into their diary.

On the morning of Day 28 (Visit 4, Last Day of First Treatment Period), subjects will not take their morning dose of IMP. They will make their morning diary entry and return to the clinic. At the clinic, weight, ECG, vital signs, a targeted physical examination, concomitant medications and adverse events will be recorded. Blood and urine samples will be taken for safety analysis. Subjects will complete assessments for Patient Reported Outcomes (interference scale of the short form BPI, SF-MPQ-2, NPSI, BDI-II, PGIC). In PK subjects, a pre-dose NPRS will be completed and a pre-dose blood sample will be taken for PK analysis.

Subjects (except PK and QST subjects) will then take their morning dose of IMP and leave the clinic. PK subjects will take their morning dose of IMP and stay for at least 6 hours. At scheduled times over this period, blood samples will be taken for PK analyses and NPRS assessments will be undertaken.

QST subjects will take their morning dose of IMP and will have specified QST parameters assessed 2 hours after this dose. An appointment for a QST assessment will be scheduled within seven days of the first dose of the second treatment period.

All subjects will take their second Day 28 IMP dose in the evening.

Washout (Days 29 to 42)

Subjects will be asked to discontinue their IMP after their evening dose on Day 28. Daily diary NPRS entries should be continued.

Second Baseline Period (Days 43 to 49)

Subjects will continue daily diary entries and will not take any IMP over Days 43 to 49 inclusive (second baseline).

Second Treatment Period (Days 50-77)

Subjects will return to the unit on Day 50 (Visit 5) with their diary completed from Days 29 to 49 inclusive. QST subjects will have a pre-dose QST assessment, if not completed within the previous 7 days.

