5.1 Overall study design

This is a randomised, placebo-controlled, double-blind, crossover, multi-site, Phase IIa study to investigate the efficacy and safety of oral LAT8881 in neuropathic pain. The overall study design is shown in Figure 4. Details of the procedures during each phase are described in Section 8.

The pharmacokinetics (PK) of LAT8881 will be investigated on Days 1, 28, 50 and 77 in 15 subjects (PK subjects) at Australian sites. Quantitative sensory testing (QST) will be performed in up to 20 subjects (QST subjects) before the first dose on Days 1 and 50 and after the morning dose on Days 28 and 77. PK subjects will not participate in QST measurements and QST subjects will not participate in PK analyses.

[figure not shown]

Figure 4: Overall study design for LAT-NP-001

Potential subjects will be required to provide written informed consent prior to any study-specific screening procedures being performed. Screening assessments will be performed from Day -28 to Day -1. Subjects deemed likely to be eligible for the trial will be given access to a diary during Screening Stage 1 and training on how to complete it from Days -7 to -1 inclusive (Screening Stage 2, first baseline period). These diary results will be reviewed on Day 1 to confirm that the subject is eligible for the study.

On Day 1, after the first baseline period, eligible subjects will be enrolled and randomised to LAT8881 or placebo. They will receive the investigational medicinal product (IMP) twice daily for four weeks (Days 1 to 28). On the morning of Day 28 they will return to the clinic for their end of first treatment visit and will take an IMP capsule in the morning during their clinic visit. They will take their final IMP dose for this treatment period in the evening.

The first treatment period will be followed by a washout period of two weeks (Days 29 to 42 inclusive) and then a second baseline period of one week (Days 43 to 49 inclusive). Over these days (i.e. Days 29-49 inclusive) subjects will not take any IMP.

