7.10 Doses and treatment regimens

Subjects will be instructed to take one capsule with water at approximately 12 hour intervals (morning and evening) at least 30 minutes before food. Once the dosing times are established, the subject should attempt to take the capsule at the same times throughout the treatment periods. If more than 16 hours has elapsed since the last dose, the dose should be missed and the next dose taken at the regular scheduled time.

Subjects will be instructed to return to the clinic on Days 28 and 77 without taking their morning dose.

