10.2.2 Pharmacokinetics

Blood samples (4 mL) will be taken pre-dose (within 30 minutes of dosing) and 2, 5, 15, 30, 60 minutes, 2, 4 and 6 hours after IMP ingestion. Blood samples will be obtained by direct venepuncture or via an indwelling cannula. Samples taken 2, 5 and 15 minutes after dosing should be within +/- 1 minute of the stated time, samples at later time points within +/- 5 minutes of the stated time.

Blood samples

will be kept on ice immediately after collection to minimise degradation and centrifuged within 60 minutes post-collection in a pre-cooled (refrigerated) centrifuge. The resulting PK plasma samples will be transferred to clean, pre-labelled polypropylene tubes and stored frozen prior to analysis. Pre-dose samples will be centrifuged separately prior to dosing.

Further details will be provided in the Laboratory Manual.

Samples will be analysed under GLP conditions by

An initial

batch of 25% of the total number of samples will be tested. If all samples tested are below the limit of quantification of the assay, further analyses will not be undertaken until the sensitivity of the assay is significantly increased.

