13.7 Analysis of pharmacokinetic data

The following pharmacokinetic parameters will be derived from the plasma concentrations of LAT8881 and metabolites, where practicable:

C_{max} Maximum plasma LAT8881 concentration

T_{max} Time to maximum plasma LAT8881 concentration

AUC_{0-t} Area under LAT8881 concentration time curve from dosing to the last observed concentration

value above the limit of quantification

AUC_{0-inf} Area under LAT8881 concentration time curve from dosing to the last observed concentration

value above the limit of quantification, extrapolated to infinity

T_{1/2} Terminal elimination half life

AUC_{0-t} will only be calculated if there are at least three quantifiable data points.

 $T_{1/2}$ will only be determined if there are at least three quantifiable elimination phase data points.

Plasma LAT8881 values below the limit of quantification will be labelled as (BLQ) in the plasma LAT8881 data listings and set to zero if recorded pre-dose.

The change in PK parameters on the last day of treatment compared with those determined after the initial dose will be investigated using a paired t-test. The mean change after repeated dosing will be presented with the corresponding 95% confidence interval and p value.

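### AUC0-inf is the only AUC named as a PK endpoint and is also applied after four weeks of twice-daily dosing, where it is not the exposure per dosing interval and rests on 6 hours of sampling

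*Protocol*

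**What the plan says.** Protocol 9.4 and SAP 7.4 list Cmax, Tmax and AUC0-inf "in each treatment period, after a single dose and at the end of four weeks treatment in PK subjects". Protocol 5.1 says that PK "will be investigated on Days 1, 28, 50 and 77 in 15 subjects (PK subjects").

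Protocol 10.2.2 takes samples pre-dose and "2, 5, 15, 30, 60 minutes, 2, 4 and 6 hours after IMP ingestion". Protocol 7.10 tells subjects to "take one capsule with water at approximately 12 hour intervals". The PK days are no exception. The synopsis states: "All subjects will take their second Day 28 IMP dose in the evening", and it says the same for Day 77.

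Protocol 13.7 derives AUC0-t and T1/2 as well as the three endpoints, so far as this is practicable. AUC0-t needs three quantifiable points. T1/2 "will only be determined if there are at least three quantifiable elimination phase data points". For AUC0-inf there is no minimum number of points, no limit on extrapolation and no fallback. Values below the limit of quantification (BLQ) are set to zero only pre-dose; post-dose BLQ handling is not stated. Last-day parameters are compared with first-dose parameters by paired t-test.

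Neither document defines an AUC over the dosing interval or over a fixed window. The SAP (section 11 introduction and section 12) leaves PK analysis to separate work.

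**The concern.** After a single dose, AUC0-inf is total exposure to that dose. After repeated dosing, the concentrations measured following the morning dose also contain what remains of earlier doses. Extrapolating them to infinity runs through a time when the next dose has already been taken. The usual measure at that stage is the AUC within one dosing interval, and the plan does not name one.

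There is also a practical difficulty. AUC0-inf needs a terminal slope, and after 1 h the only samples are at 2, 4 and 6 h. If elimination is slow, much of the figure is extrapolated. If it is fast, or levels are near the assay limit, the slope may not be estimable.

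At stake is the secondary objective on PK after a single dose and after four weeks (Protocol 4.2; SAP 3.2, item 12), together with the 13.7 paired comparison. For AUC0-inf, that comparison can use only subjects with a usable value on both days. A reader could also take ordinary accumulation for a change in the drug's kinetics.

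**Working it through.** The documents state no half-life, extrapolation limit or PK precision, so there is no figure of theirs to reproduce.

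**Inputs from the documents.** Last sample at 6 h (Protocol 10.2.2); dosing interval about 12 h (7.10); 15 PK subjects (5.1).

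**Assumptions.** Linear, mono-exponential kinetics with rapid absorption; steady state by Day 28/77; half-life h of 1 to 6 hours.

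**Formulas.**
- Share of AUC0-inf extrapolated beyond 6 h: 2^(−6/h).
- At steady state every concentration is the single-dose value times R = 1/(1 − 2^(−12/h)). AUC0-12 at steady state equals single-dose AUC0-inf, so Day 28/77 AUC0-inf exceeds AUC0-12 by R − 1 = 1/(2^(12/h) − 1).
- Part of steady-state AUC0-12 that is observed by 6 h: (1 − 2^(−6/h))/(1 − 2^(−12/h)) = 1/(1 + 2^(−6/h)).

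Example at h = 3: the extrapolated share is 2^(−2) = 25%; the excess is 1/(16 − 1) = 6.7%; the observed part is 1/1.25 = 80%.

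| Assumed half-life | Extrapolated beyond 6 h | Excess of AUC0-inf over AUC0-12, Days 28/77 | AUC0-6h as part of AUC0-12, Days 28/77 |
|---|---|---|---|
| 1 h | 1.6% | 0.02% | 98% |
| 2 h | 12.5% | 1.6% | 89% |
| 3 h | 25% | 6.7% | 80% |
| 4 h | 35% | 14% | 74% |
| 6 h | 50% | 33% | 67% |

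**Thresholds.** The extrapolated share passes 20% (an assumed limit, not in the documents) at h = 6/log2(5) = 2.6 h. The excess passes 5% at h = 12/log2(21) = 2.7 h and 25% at h = 12/log2(5) = 5.2 h.

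**Sensitivity.** With first-order absorption (assumed absorption half-life 0.1 to 0.5 h), the single-dose extrapolated share is 13–17% at h = 2, 26–30% at h = 3 and 51–54.5% at h = 6. The excess is 1.7–2.1%, 6.9–8.0% and 34–36%. The picture does not change.

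**Effect on the paired comparison.** With unchanged kinetics, the last-day/first-dose ratio of AUC0-inf is R: 1.00, 1.02, 1.07, 1.14 and 1.33 down the table. The ratio of AUC0-6h is the same R in this model. The ratio of Day 28/77 AUC0-12 to first-dose AUC0-inf is 1.00.

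**Points for the slope.** A peak at 1 h leaves three later samples (2, 4, 6 h). A peak at 2 h leaves two if the peak is excluded from the fit, and three if it is included.

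**The case against.** The strongest reply is that the problem may be negligible. Sampling at 2, 5 and 15 minutes suggests that fast kinetics were expected, and at half-lives of 1 to 2 h both effects are small. The documents give no half-life, and clinical detail is left to the Investigator's Brochure. This stands: the size is unknown.

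Several stronger readings are tempting, and the text does not support them:
- A reader might infer that AUC0-inf is the only exposure endpoint. Cmax is in the same list, and 13.7 also derives AUC0-t.
- A reader might infer that AUC0-inf must be produced for everyone. Protocol 13.7 derives parameters only where practicable, although it does not say what replaces a missing value.
- A reader might infer that a peak at 2 h or later rules out AUC0-inf. The three-point rule is written for T1/2 alone, and the plan does not say whether the peak enters the fit.
- A reader might take 10.2.2 to predict BLQ samples. It is a contingency for an initial 25% batch that is entirely BLQ; in that case AUC0-6h would fail too.

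It is also fair to say that AUC0-6h carries the same accumulation ratio as AUC0-inf and is not the exposure per interval, and that AUC0-t equals AUC0-6h whenever the 6 h sample is quantifiable. Both are true. AUC0-6h therefore serves only as a comparison over the same window on both days that needs no terminal slope; a separate AUC0-12 is needed for exposure per interval.

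Finally, the separate PK analysis may hold slope, BLQ and extrapolation rules. That could settle the missing detail, but not the endpoint named in 9.4 and SAP 7.4.

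**Conclusion.** The point holds in a limited form. AUC0-inf on Days 28/77 is the wrong parameter for exposure per dosing interval. This follows from its definition and the 12-hourly schedule; only its size depends on the half-life. The excess over AUC0-12 is under 2% at 1 to 2 h, about 7% at 3 h and 33% at 6 h, assuming mono-exponential, linear kinetics at steady state.

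The extrapolated share is 2 to 12.5%, 25% and 50% at the same half-lives. Values may therefore be unreliable or missing in some of the 15 subjects. The documents do not show that this would happen often, or which kind of subject would drop out of the paired test.

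The matter concerns a secondary objective and leaves the primary endpoint untouched. It deserves correction because the correction needs no new samples.

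**What to change.** Amend Protocol 9.4 and 13.7, SAP 7.4 and the separate PK plan:

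1. Use AUC0-6h on both days for the paired first-versus-last-day comparison and describe the result as accumulation over that window. State how post-dose BLQ values are handled, and use the linear rule for any segment that ends at zero, since a logarithmic rule is undefined there.
2. On Days 28/77, replace AUC0-inf with AUC0-12, using that day's pre-dose sample as the 12 h trough under a steady-state assumption.
3. Keep AUC0-inf for the first LAT8881 dose only (Day 1 or Day 50, by sequence), as supportive. Report the extrapolated share and set a limit for it in advance.

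The cost is wording; all the samples are already planned. The limitations should be stated. AUC0-6h is partial if elimination is slow (67% of AUC0-12 at a 6 h half-life). AUC0-12 relies on steady state and on the pre-dose sample lying close to 12 h after the previous evening's dose; the morning dose is held until the clinic visit on those days, so the actual gap should be checked.

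While editing, check the SAP 5.2 footnotes, which read as up to 8 hours of PK sampling in the second period, against 6 hours in SAP 5.1 and the protocol. This may be only an extraction error in the text.

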9.5 Exploratory endpoints

- Association between change in mean NPRS from baseline to the end of four weeks treatment and selected subject baseline characteristics, including clinical diagnosis and pre-treatment QST parameters
- Change from baseline in specified QST parameters to the end of 4 weeks treatment, in each treatment period
- Correlation between plasma LAT8881 concentration and the change in mean NPRS from baseline to the end of four weeks treatment in PK subjects
- Change in mean NPRS score from baseline to the last week of each treatment period, after omission of subjects with the 25% most variable first baseline NPRS scores

10. Study measurements

10.1 Clinical assessments

10.1.1 Medical history

The medical history will include any conditions reported by the subject or noted by the investigator in each body system, including allergies or drug sensitivities, past surgeries and any history of substance abuse (drug or alcohol) and will be recorded at screening. A review of the subject's medication use will also occur.

A diagnosis of shingles or diabetes and the date (month/year) at which PHN or DPN was first reported should be confirmed by an independent source (e.g. general practitioner, hospital records).

10.1.2 Demographics

Demographic information will include the subject's age, gender and ethnic affiliation.

10.1.3 painDETECT questionnaire

The PD-Q consists of seven pain sensory symptom items (burning, tingling/prickling, light touching, sudden pain attacks/electric shock-type pain, cold/heat, numbness, slight pressure), one pain course pattern item, and one pain radiation item. From this questionnaire, a PD-Q total score, ranging from -1 to 38 is calculated. A total score ≥19 indicates a neuropathic component is likely, ≤12 indicates a neuropathic component is unlikely and scores 13-18 are considered uncertain i.e. a neuropathic pain component can be present. The English version of the PD-Q is widely used and is reported to be reliable as a screening tool for neuropathic pain, although it has yet to be fully validated. The indicates a screening tool for neuropathic pain, although it has yet to be fully validated.

The PD-Q will be used in conjunction with clinical assessment to facilitate diagnosis of neuropathic pain.

10.1.4 Electrocardiogram

12-lead ECGs will be performed with subjects lying in a supine or semi-supine position for at least 5 minutes prior to measurement. All ECG tracings will be reviewed by the Investigator or an appropriately medically qualified reviewer designated this responsibility by the Investigator.

10.1.5 Vital signs

Resting supine or semi-supine blood pressure (systolic and diastolic), heart rate, and respiratory rate will be evaluated. The same arm should be used throughout the study. Body temperature (tympanic), will also be evaluated as part of vital signs.

Subjects should be resting in a supine position for at least 5 minutes prior to and during vital signs measurement.

10.1.6 Physical examination

Physical examinations are to be performed by a medically qualified physician according to their standard medical practice. Any new or worsening abnormality, clinical sign or finding must be documented.

A full physical examination is to be performed at the first screening visit. At other scheduled time points, a targeted (symptom directed) physical examination, as clinically indicated, is to be performed. All physical examinations will include assessment of the area of pain.

[figure not shown]
A full physical examination will include assessments of the head (eyes, ears, nose, mouth, throat), skin, neurological system, respiratory system, cardiovascular system, musculoskeletal system, abdomen (liver and spleen), lymph nodes and extremities, general appearance, and any additional assessments needed to establish baseline status or change from baseline or evaluate symptoms or adverse events.

Neuropathies other than PHN and DPN will be excluded by clinical assessment at screening. Nerve conduction studies are not required for this assessment.

10.1.7 Height and weight

Height (centimetres) and weight (kilogram), without shoes, will be measured at the screening visit and BMI calculated. Weight (without shoes) will be measured at all other visits.

10.1.8 QST phenotype

Full details of the QST procedures will be provided in the QST manual.

10.2 Laboratory assessments

10.2.1 Clinical safety testing

Blood and urine samples will be taken at screening, on Days 1, 28, 50, 77 and at the end of study visit. Blood samples will be tested at one nominated laboratory per study site. Urinalysis (dipstick) will be performed at the investigational site.

Details of the volume of blood and type of tubes required for the following tests will be provided in the Study Manual. At the investigator's discretion, sample collection may be repeated if an abnormal result occurs due to technical or other reasons.

The following tests will be performed.

